2. Identify putative psychological mechanisms of response to CPT through pre-, mid-, and post-intervention measures of PTSD severity as well as measures of hopelessness, self-blame, and negative self-related thoughts.

Hypotheses:

NIMH Branch:

1. It is predicted that feasibility will be established by obtaining $\geq 80\%$ participant retention for the CPT course. As additional metrics of feasibility we will assess eligibility;

[†]For the NIMH branch, any historical data (i.e., information that is stable and is not expected to change over time) that has already been collected through protocol 2014-1106, we will obtain this data from the PI's database (2014-0350) and will not re-administer these assessments under the current protocol.

- participation; compliance; adherence; competence; and safety.
2. It is predicted that group CPT acceptability will be established by obtaining mean scores ≥ 27 on the CSQ-8.
 3. It is predicted that assessment collection feasibility will be established by obtaining 100% of PCL-5s at each timepoint for participants retained at that timepoint.

WPP Branch:

1. It is predicted that compared to the active control group, the CPT group will exhibit significantly greater reductions in PTSD symptom severity (primary outcome measure) as well as reductions in the severity of depression and general anxiety symptoms (secondary outcome measures) over the course of treatment.
2. It is predicted that the CPT group will exhibit greater reductions in hopelessness, self-blame, and negative self-related thoughts compared to the active control group.
 - a. Within only the CPT group, the reductions in hopelessness, self-blame, and negative self-related thoughts will precede the reduction in PTSD symptoms.
 - b. Within only the CPT group, the reduction in PTSD symptom severity will be mediated by reductions in hopelessness, self-blame, and negative self-related thoughts.

Trainee Project:

This study is part of the dissertation project of [name].

Participants:

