Participants will be eligible to participate if they meet the following criteria: 18 years of age or older; IQ greater than or equal to 70; reading level of 4th grade or higher; no active symptoms of psychosis that would interfere with the individual's ability to participate in the group, no active suicidal ideation with intent or plan, able and willing to participate in group therapy; no scheduled release date before the end of the treatment group; and not currently enrolled in trauma focused treatment that is historical or involves processing of trauma itself. Other vulnerable populations within the prison setting (i.e., pregnant women or individuals appearing to lack the capacity to provide informed consent) will not be eligible for participation. Research suggests that a PCL-5 score between 31-33 indicates a probable diagnosis of PTSD. Accordingly, participants will be eligible to participate if they score a 31 or greater on the PCL-5 within two months of starting the study treatment. We will identify participants meeting these eligibility criteria from the pool of subjects who have previously participated in another IRB-approved protocol led by PI [name] (2014-1106).

WPP Branch:**Taycheedah Correctional Institution:**

Participants will be eligible to participate if they meet the following criteria: 18 years of age or older; no serious self-harm past 6-months (in clinical observation due to self-harm), no disciplinary segregation time in past 6-months, have not participated in the previous CPT groups with UW Project (NIMH branch), no active symptoms of psychosis that would interfere with the individual's ability to participate in the group, no active suicidal ideation with intent or plan, able and willing to participate in group therapy; not currently enrolled in trauma focused treatment that is historical or involves processing of trauma itself; no scheduled release date before the end of the treatment group; and able to understand the consent form as measured by the consent quiz. Research suggests that a PCL-5 score between 31-33 indicates a probable diagnosis of PTSD. Accordingly, participants will be eligible to participate if they score a 31 or greater on the PCL-5 within two months of starting the study treatment. We will identify participants meeting these eligibility criteria from the DOC list of residents on the waitlist for trauma treatment.

Kettle Moraine Correctional Institution:

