Each CPT group will enroll 6-8 members and will meet weekly or biweekly for 12 group sessions including one follow up CPT session. Participants will be referred to by their preferred first names. The CPT protocol will follow the published manual [15]. Session 1 begins with orientation to group treatment and group rules, education about PTSD, an overview of treatment, and an assignment to write an impact statement about the personal meaning and effect of the traumatic event. After reading and discussing the meaning of the traumatic event in Session 2, group members are introduced to the identification of and relationship among events, thoughts, and emotions. At the end of Session 3, group members are given the assignment of recording events, thoughts, and emotions throughout the week to establish the relationships between thoughts and emotions within their own lives. During Session 4, cognitive therapy begins with Socratic questions regarding self-blame and other distortions regarding the event. In Sessions 5-6, the focus of the therapy shifts to teaching clients to challenge and change their beliefs about the meaning of the event and the implications of the trauma for their lives. Group members are first taught to challenge a single thought by asking themselves a series of questions. They are then taught to identify problematic patterns of cognitions that have come to represent a style of responding. From that point, beginning with Session 7, group members use worksheets that incorporate the earlier activities as well as the development of alternative, more balanced self-statements. In Sessions 7-12, group members are asked to focus on one of the five core themes of CPT each week (safety, trust, power/control, esteem, or intimacy) and correct any overgeneralized beliefs related to that theme. In Session 11, group members are asked to rewrite their impact statements to reflect their current beliefs, and these revised statements are then used in Session 12 to evaluate gains made in treatment and areas in which they wish to continue working. Following the completion of the 12 CPT sessions, an additional follow-up group CPT therapy session will be provided. This follow-up CPT session is recommended by the CPT manual and typically occurs 2-3 months after the end of the 12-session treatment group. The group follow-up CPT session is designed to check-in with participants to see how they are doing, work through any problems/difficulties they have had, and to reinforce the strategies and skills they learned from the treatment group. At the start of each treatment session, the participants will be asked to complete the PCL-5. At the end of treatment sessions, participants will be given the option to de-stress for 15-20 minutes.

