Specific Aim #1: Our assessment of feasibility of the interventions will be determined by measures of eligibility, participation, retention (primary measure), compliance with intervention activities, adherence to intervention elements, competence of intervention elements, and safety.

Primary Outcome Measure:

Retention will be measured as the percentage of residents attending all 12 sessions. Retention rates for CPT in non-incarcerated samples are typically 80% or less [15]; hence, our study goal is $\geq 80\%$ retention. Retention is our primary measure of feasibility for this aim.

Secondary Outcome Measures:

Eligibility will be measured as the percentage of participants who meet the full set of inclusion criteria. We will also compute the percentages of participants who are excluded for each individual criterion separately, so we are able to discern the relative impact of each criterion on study eligibility.

Participation will be measured as the percentage of eligible participants agreeing to

participate. Our study goal is $\geq 75\%$ participation of eligible participants.

Compliance will be measured as the percentage of retained participants performing intervention activities during session (e.g., attending to and contributing to the discussion); the percentage of participants completing the homework assignment each week; and the percentage of participants fully completing the pre-, mid-, and post-intervention assessment batteries. Our study goal is $\geq 80\%$ compliance of participants-retained in the study.

Adherence by the therapists will be measured by ratings of the presence or absence of five session elements (scores 0-5) by the clinical supervisors, as in previous CPT studies [16, 18]. Adherence ratings will be collected for two audiotaped group sessions out of each 12-session intervention (16.7% of sessions). Our study goal is adherence scores ≥ 4 for each session.

Competence of the therapists will be measured by ratings of the quality of session elements (scores 1-7; 1="not satisfactory", 4="satisfactory", 7="excellent") by the clinical supervisors, as in previous CPT studies [16,18]. Competence ratings will be collected for two audiotaped group sessions out of each 12-session intervention (16.7% of sessions). Our study goal is competence scores ≥ 4 for each session.

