Safety will be measured through the suicidal ideation item on Beck Depression Inventory-II [34], administered at the pre-, mid-, and post-intervention assessments. Participants who endorse current suicidal ideation will be referred to mental health services within the institution.

In sum, we will consider the study successful in terms of feasibility if we meet the following thresholds for each intervention: participation rate $\geq 75\%$ of eligible participants; retention rate $\geq 80\%$ of participating participants; compliance rate $\geq 80\%$ among retained participants; adherence scores ≥ 4 ; competence scores ≥ 4 ; and $\leq 10\%$ of participating participants reporting an increase in suicidal ideation.

Specific Aim #2: Our assessment of acceptability of the interventions will be determined through measures of client satisfaction and reasons for treatment dropout.

Primary Outcome Measure: Acceptability will be measured by client satisfaction using participant scores on the CSQ-8. Other studies of CPT [44] have established acceptability of interventions using the CTQ-8 when mean scores are ≥ 27 ; hence, our study goal is scores of ≥ 27 on the CTQ-8. Client satisfaction is our primary measure of feasibility for this aim.

Secondary Outcome Measures: Reasons for discontinuation of treatment will be measured through participant self-report.

We will consider the study successful in terms of acceptability if client satisfaction mean ratings

are ≥ 27 on the CTQ-8.

Specific Aim #3: Our assessment of feasibility of assessment distribution will be determined through measures of assessment completion.

Primary Outcome Measure:

Assessment completion will be measured as the percentage of PCL-5 at each timepoint for the number of participants retained at that timepoint.

We will consider the study successful in terms of assessment distribution feasibility if 100% of PCL-5 assessments at each timepoint are completed for each participant retained at that timepoint.

WPP Branch:

Specific Aim #1: To assess preliminary efficacy, we will collect primary and secondary outcome data at the pre-, mid-, and all post-intervention time points.

Primary Outcome Measure:

PTSD symptom severity will be measured with the PTSD Checklist for DSM-5 (PCL-5) [33].

Secondary Outcome Measures:

Depression symptom severity will be measured with the BDI-II [34]. Anxiety symptom severity will be measured with the BAI [35].

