Regarding criterion (i), this study is designed to identify psychological and affective factors that may predispose a person to criminal behavior and incarceration in order to effectively design and implement treatment programs. Specifically, PTSD severity has been linked to increased risk of recidivism, and trauma is a hypothesized precursor to criminality [2,3,10].

Statistical Considerations:

NIMH Branch:

The primary goal of this study is to establish feasibility of the target intervention (CPT). Hence, we base our power analysis on the “retention” data collected Specific Aim #1 (i.e., the percentage of participants completing the CPT intervention). A sample size of $n = 32$ for the CPT group will provide 80% power to perform a one-sided test where the null hypothesis is 60% retention (approximately the lowest retention rate reported in previous CPT trials, versus the alternative hypothesis of 80% retention (our study goal), with a Type I error of 5%.

WPP Branch:

The primary goal of this study is to examine efficacy of the target intervention (CPT). Therefore, we will use the same target sample size ($n = 32$) used to establish feasibility of the target intervention, as this reflects the number of participants needed to conduct powered analyses based on the lowest retention rate reported in previous CPT trials.

Both the NIMH and WPP branches satisfy this condition with sample sizes of $n = 60$ for the CPT groups and sample sizes of $n = 60$ for control groups (WPP branch only).

REFERENCES

1. James, D. J., Glaze, L. E., & Statisticians, B. (2006). *Bureau of Justice Statistics Special Report Highlights Mental Health Problems of Prison and Jail Inmates*.
4. Kessler, R. C., Wai, T. C., Demler, O., & Walters, E. E. (2005). Prevalence, severity, and comorbidity of 12-month DSM-IV disorders in the National Comorbidity Survey Replication. In *Archives of General Psychiatry* (Vol. 62, Issue 6, pp. 617–627). <https://doi.org/10.1001/archpsyc.62.6.617>

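### The NIMH branch's 80% power is for a test against 60% retention that no feasibility criterion uses; the deciding criterion, observed retention of at least 80%, is met only 52–58% of the time if true retention is 80%

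*Combined protocol and SAP*

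**What the plan says.** All references are to the combined protocol and SAP.

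- **Statistical Considerations, NIMH Branch.** The power analysis is based on retention. A sample of 32 "will provide 80% power to perform a one-sided test where the null hypothesis is 60% retention", "versus the alternative hypothesis of 80% retention (our study goal"), with a 5% type I error. The same section later gives 60 as the CPT group size, while the NIMH Branch paragraph on participant numbers gives 72.
- **Hypotheses, NIMH Branch.** "It is predicted that feasibility will be established by obtaining" retention of at least 80%.
- **Measurement of Specific Aims, NIMH Specific Aim #1.** Retention means attendance at all 12 sessions, with a goal of at least 80%. "Retention is our primary measure of feasibility for this aim". The goal is motivated by the remark "Retention rates for CPT in non-incarcerated samples are typically 80% or less".
- **Same aim, closing summary.** "In sum, we will consider the study successful in terms of feasibility if we meet the following thresholds for each intervention"; the list that follows includes retention of at least 80% alongside participation, compliance, adherence, competence and safety limits.

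The 60% null appears only in the power statement. No criterion says that rejecting 60% establishes feasibility, and the plan does not explain how the test relates to the goal.

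**The concern.** The power statement is the only probability the plan attaches to its primary feasibility aim. A reader will naturally take it as the chance of success if retention is as good as hoped. It is not, because the rule that decides the aim is a different one, with its threshold set at the assumed true value. Such a rule is met roughly half the time whatever the sample size.

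Two things are at stake. The stated assurance overstates how likely the plan is to meet its own goal. The plan also leaves open how to describe a result that excludes 60% but falls short of 80%, so that wording could be chosen after the data are seen.

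**Working it through.** **Inputs.** From Statistical Considerations: n = 32, null 0.60, alternative 0.80, one-sided α = 0.05, and NIMH group size 60. From the participant-numbers paragraph: 72. From the Hypotheses and Specific Aim #1: observed retention of at least 80%. Assumption: participants are independent.

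**Step 1: reproduce the stated power at n = 32.**

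- Normal approximation: Φ{[0.20·√32 − 1.645·√(0.6·0.4)] / √(0.8·0.2)} = Φ{(1.131 − 0.806)/0.4} = Φ(0.814) = 79.2%. The n for exactly 80% power is 32.6.
- Arcsine: h = 2·asin√0.8 − 2·asin√0.6 = 0.442; Φ(0.442·√32 − 1.645) = Φ(0.856) = 80.4%. The n for exactly 80% power is 31.6.
- Exact binomial: the smallest cut that holds 5% is 25/32 (α = 2.5%), with power 69.8%. A cut of 24/32 has α = 5.7% and power 82.5%.

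The plan's 80% is therefore reproduced by either usual approximation.

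**Step 2: chance of meeting the goal.** The count needed is c = ⌈0.8n⌉, and the chance is P(X ≥ c) with X ~ Binomial(n, p).

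| n | Count needed | p = 60% | p = 75% | p = 80% | p = 85% | True p for an 80% chance |
|---|---|---|---|---|---|---|
| 32 | 26 | 0.9% | 27.8% | 53.5% | 80.5% | 84.9% |
| 60 | 48 | 0.08% | 23.2% | 57.6% | 89.4% | 83.2% |
| 72 | 58 | 0.02% | 17.1% | 52.4% | 88.6% | 83.5% |

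The differences between sizes at p = 80% are mostly rounding of the count needed. Over every n from 32 to 72 the figure stays between 47% and 60%. The closing summary also requires the other thresholds, so overall feasibility success cannot be more likely than these figures.

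**Step 3: chance of the in-between result at true 80%.** This is the exact power against 60% minus the chance of meeting the goal. Every count that meets the goal also passes the test, so the difference is exact.

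| n | Test cut (α) | Power at 80% | Minus goal met | Excludes 60%, misses 80% |
|---|---|---|---|---|
| 32 | 25 (2.5%) | 69.8% | 53.5% | 16.3% |
| 60 | 43 (4.1%) | 95.7% | 57.6% | 38.1% |
| 72 | 51 (3.8%) | 97.8% | 52.4% | 45.4% |

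At n = 32 with the cut of 24, the in-between figure is 82.5% − 53.5% = 29.0%.

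**The case against.** The strongest reply is that the plan states no wrong number. It ties the 80% power explicitly to the test of 60% against 80%, calls 80% its goal in the same sentence, and never claims an 80% chance of reaching that goal. A feasibility target is a benchmark and need not carry high assurance. All of this stands as far as it goes. Sharing the value 80% does not make the test the decision rule, though, and a plan that bases its power analysis on retention should say which rule the power describes.

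The goal is also the stricter rule. Meeting it always passes the exact test, and at true 60% it is met at most 0.9% of the time. A reader might infer that the mismatch risks declaring feasibility falsely. The figures show the opposite risk, of missing the goal.

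A reader might also infer from "Retention rates for CPT in non-incarcerated samples are typically 80% or less" that about half is the best chance available. That remark concerns other populations, is not a bound for this one, and is not shown to use the all-12-session definition. At true 85% the goal is met 80–89% of the time.

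Finally, the in-between result is less prominent at the powered size (16% at n = 32 with the exact cut) than at 60 or 72, where much of the larger figure comes from the actual n exceeding the powered n.

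**Conclusion.** The concern holds as a minor point of disclosure and reporting. The 80% power is correct by approximation for excluding 60% retention, but it does not describe the criterion that decides the primary aim. That criterion has a 54%, 58% or 52% chance of being met at n = 32, 60 or 72 if true retention is 80%.

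These figures assume independent participants. CPT is delivered in groups ("Each CPT group will enroll 6-8 members and will meet weekly or biweekly for 12 group sessions"), and the documents give no intraclass correlation, so no clustered figures are offered here.

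It is tempting to conclude that a shortfall would mark the programme as infeasible or hold up the WPP branch. The documents do not support that. The plan never says that retention below 80% means infeasible, and its introductory description of the two branches lets WPP begin at a facility once NIMH is completed there, not once it succeeds.

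**What to change.** 1. **Statistical Considerations, NIMH Branch.** State that the 80% power is for excluding 60% retention, not for meeting the observed-80% goal. Beside it, give the chance of meeting the goal at true 80% for the agreed n.
2. **Specific Aim #1.** Keep the 80% goal and the all-12-session endpoint. Report observed retention with a 95% CI and the one-sided test against 60%, labelled as assuming independence unless therapy-group clustering is allowed for. Describe a result that rejects 60% but falls below 80% as *goal not met, 60% excluded*.
3. **Sample size.** Settle on one NIMH n (60 or 72) and quote the figures for it.

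The cost is a few sentences and a choice of interval and test method. No extra participants or data are needed, and no threshold changes. The drawback is that the stated assurance for the primary aim becomes less favourable. Because the WPP eligibility criteria already refer to people who "have not participated in the previous CPT groups with UW Project (NIMH branch"), the added wording should be dated and should say whether NIMH retention data had been seen.
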